Total Study-Wide Enrollment Goal: 71 **Greater than 25% of the overall study accrual will be at DF/HCC:** Yes No
Total DF/HCC Estimated Enrollment Goal: 56 **Adult Age Range:** 18+ **Pediatric Age Range:** N/A
Will all subjects be recruited from pediatric clinics? Yes No
If enrolling both adults and pediatric subjects, anticipated percent of pediatric subjects: N/A
Retrospective Medical Record Reviews only (Please provide date range): from to

6. DF/HCC PARTICIPANTS UNDER DFCI IRB (check all that apply)

- | | |
|---|---|
|  Beth Israel Deaconess Medical Center (BIDMC) |  DF/BWCC in Clinical Affiliation with South Shore Hospital (DFCI @ SSH) |
|  Beth Israel Deaconess Medical Center – Needham (BIDMC-Needham) |  Dana-Farber at Milford Regional Cancer Center (DFCI @ MRCC) |
|  Boston Children's Hospital (BCH) |  Dana-Farber at Steward St. Elizabeth's Medical Center (DFCI @ SEMC) |
|  Brigham and Women's Hospital (BWH) |  Massachusetts General Hospital (MGH) |
|  Dana-Farber Cancer Institute (DFCI) |  Mass General/North Shore Cancer Center (MGH @ NSCC) |
|  Dana-Farber/New Hampshire Oncology-Hematology (DFCI @ NHOH) |  Mass General at Emerson Hospital – Bethke (MGH @ EH) |
| |  New England Cancer Specialists (NECS) |

7. NON-DF/HCC PARTICIPANTS UNDER DFCI IRB (check all that apply)

- | | |
|---|--|
|  Cape Cod Healthcare (CCH) |  Broad Institute |
|  Lowell General Hospital (LGH) |  Lawrence & Memorial Cancer Center in affiliation with Dana-Farber |
|  New Hampshire Oncology-Hematology-P.A. (NHOH) | Community Cancer Care (LMCCC) |
|  Newton-Wellesley Hospital (NWH) | |

Protocol Front Sheet

10/02/13	Consent Form and Front Sheet replaced due to Amendment #21	10/02/13	10/02/13
10/03/13	Consent Form, Protocol and Front Sheet replaced due to Amendment #23	09/30/13	10/02/13
10/09/13	Correction: Consent Form replaced due to incorrect version previously provided w/ Am #23	09/30/13	10/08/13
10/17/13	Front Sheet replaced due to Amendment #25	10/15/13	n/a
10/24/13	Protocol and Nursing PES replaced, Alert Page removed due to Amendment #24	10/08/13	N/A
11/13/13	Protocol, Consent Form and Front Sheet replaced due to Amendment #26	11/07/13	11/13/13

11/26/13	Correction: Consent Form replaced due to incorrect version previously provided w/ Am #26	11/07/13	11/26/13
01/27/14	Consent Form replaced due to Continuing Review #2	01/23/14	01/24/14
02/12/14	Alert Page added due to Amendment #27	01/23/14	N/A
03/18/14	Consent Form, Protocol and Front Sheet replaced due to Amendment #28 (Note: re-consent required)	02/25/14	03/18/14
04/02/14	Protocol, Pharmacy Manual-300 mg and Front Sheet replaced due to Amendment #29	03/24/14	N/A
04/04/14	Correction AM #29: Alert Page removed	N/A	N/A
04/04/14	Update: PES replaced	N/A	N/A
04/15/14	Alert Page added due to Amendment #30	04/09/14	n/a
05/14/14	Alert Page and Front Sheet replaced due to Amendment #31	05/02/14	N/A
06/03/14	Front Sheet replaced due to Amendment #32	06/02/14	n/a
07/25/14	New Hampshire Oncology – Hematology site closed to new accrual; All other sites remain open to accrual; Amendment # 33 (Effective 06/30/14)	07/01/14	N/A
08/14/14	Administrative Update #1: Pharmacy manuals 400mg and 300mg replaced with Pharmacy Manual	N/A	N/A
10/07/14	Protocol, Front Sheet , Nursing PES replaced due to Amendment #34	09/30/14	N/A
10/14/14	Correction Amendment #34: Alert Page removed	N/A	N/A
11/11/14	BIDMC removed from the study. Consent Form and Front Sheet replaced due to Amendment #35	11/10/14	N/A
01/05/14	Consent Form replaced due to Amendment #36	12/22/14	12/23/14
01/22/15	Study renewal / Consent Form footer replaced due to Continuing Review #3	01/08/15	N/A
05/18/15	Protocol, Consent Form and Front Sheet replaced due to Amendment #37	05/15/15	05/18/15
Date Posted	Revised Sections	IRB Approval Date	OnCore Version Date
10/20/15	Front Sheet replaced due to Amendment #38	10/16/15	N/A
12/28/15	Study renewal / Consent Form footer replace due to Continuing Review #4	12/17/15	12/18/15
01/06/16	Protocol, Consent Form and Front Sheet replaced due to Amendment #39	12/29/15	01/05/16

1. OBJECTIVES

1.1 Study Design

This is a randomized phase II trial of fulvestrant alone or in combination with ganetespib (STA-9090) (a novel HSP-90 inhibitor) in patients with hormone receptor-positive, metastatic breast cancer.

1.2 Primary Clinical Objective

The primary objective of this trial is to evaluate the effect of the addition of ganetespib to fulvestrant on progression-free survival (PFS), compared to fulvestrant alone.

1.3 Secondary Clinical Objectives

- To assess the safety and tolerability of ganetespib in combination with fulvestrant
- To describe and compare the objective response rate by RECIST 1.1 between arms, limited to patients with measurable disease at baseline.
- To describe and compare the clinical benefit rate, defined as complete response (CR) + partial response (PR) + stable disease \geq 6 months between arms
- To describe and compare overall survival (OS) between arms

1.4 Correlative Objectives

1.4.1 The primary correlative objective is to test whether high nuclear expression of HSF1 (as assessed on archival breast tumor samples) is associated with PFS, separately in the fulvestrant only arm and the combination arm.

For this analysis, we will assay existing archival breast tumor specimens. Metastatic specimens will take priority over primary tumor specimens; however both should be collected when available. We hypothesize that high nuclear expression of HSF1 may be associated with worse progression-free survival in patients treated with fulvestrant alone. In patients treated with the combination of fulvestrant + ganetespib, we hypothesize that because high nuclear expression of HSF1 may be indicative of increased dependence on the heat shock network, it may be associated with improved PFS.

1.4.2 All other correlative objectives are exploratory and hypothesis-generating only. They are listed below:

- We will collect cycle 2 biopsies (required in patients with biopsy-accessible disease, see Section 3.1.14 and Section 8.1) to assess the effect of fulvestrant alone versus fulvestrant plus ganetespib within tumor specimens. Using a Nanostring custom code set, we will assess a set of genes regulated by HSF1, the major transcriptional regulator of inducible expression for the entire heat shock network. We will also

CONFIDENTIAL

This document is confidential. Do not disclose or use except as authorized.

assess a panel of estrogen and ER-regulated genes, other downstream targets of Hsp90, and genes thought to play a role in malignant progression/endocrine resistance.

We will compare cycle 2 biopsy specimens between patients treated with fulvestrant alone versus those treated with fulvestrant + ganetespib. We will use a cutoff of 4-fold increase or decrease relative to standard reference genes to characterize the expression of each of the selected genes (upregulated, downregulated, or neutral) for comparison between groups.

- We will tabulate the expression of the same set of genes as specified above (by Nanostring custom gene set), categorized as above (upregulated, downregulated, neutral), in archival specimens (primary and metastatic, as available), cycle 2 tumor biopsies, and optional time-of-progression tumor biopsies, in order to describe the stability of these markers over time
- Using the cycle 2 biopsies (required in patients with biopsy-accessible disease, see Section 3.1.14 and Section 8.1), we will also compare the expression of ER, PR, AR, HSF1, HER2, and EGFR by immunohistochemistry and amplification of EGFR and HER2 using fluorescence in situ hybridization (FISH) to assess the effect of fulvestrant alone versus fulvestrant plus ganetespib within tumor specimens.

For this analysis, each of the markers will be described as “positive” or “negative”. For ER, PR, AR, and EGFR, “positive” will include “high positive”, defined as $\geq 10\%$ nuclear staining, and “low positive” will be defined as 1-10% nuclear staining, and “negative” will be defined as no staining or only rare cells positive. For HSF1, “positive” will be defined as 2+ staining, and “low/negative” will include “low-positive” (1+ staining), and true negatives (no staining or rare cells positive) (Santagata et al, manuscript in preparation). For HER2, we will use the standard 0-3+ scale, but will dichotomize with 0, 1+, and 2+ being negative and 3+ positive.

For this analysis, FISH ratio ≥ 2.0 will be considered positive. FISH ratio < 2.0 will be considered negative.

- We will tabulate the expression of ER, PR, AR, HSF1, HER2, and EGFR by immunohistochemistry in archival specimens (primary and metastatic, as available), cycle 2 tumor biopsies, and optional time-of-progression tumor biopsies, in order to describe the stability of these markers over time.
- We will tabulate the amplification status of EGFR and HER2 using fluorescence in situ hybridization (FISH) in archival specimens (primary and metastatic, as available), cycle 2 tumor biopsies, and optional time-of-progression tumor biopsies, in order to describe the stability of these markers over time.
- We will describe ER, PR, AR, and HSF1 expression (using the same cutoffs as above) and describe HER2/EGFR amplification (using the same cutoffs as above) in

CONFIDENTIAL

This document is confidential. Do not disclose or use except as authorized.

circulating tumor cells (CTCs) pre-therapy, Cycle 2 Day 8, Cycle 2 Day 9, and at time of progression, separately by arm of treatment.

- We will explore the relationship between EGFR and/or HER2 amplification in baseline CTCs and PFS, in each arm separately.
- We will compare ER, PR, AR, HSF1 expression, and HER2 and EGFR amplification status on cycle 2 Day 9 on-study biopsy and Cycle 2 Day 9 CTCs.
- We will collect peripheral blood mononuclear cells (PBMC) pre-therapy, Cycle 2 Day 8, Cycle 2 Day 9, and time of progression. Using a Nanostring custom code set, we will assess a set of genes regulated by HSF1, the major transcriptional regulator of inducible expression for the entire heat shock network. We will also assess a panel of estrogen and ER-regulated genes, other downstream targets of Hsp90, and genes thought to play a role in malignant progression/endocrine resistance. We do not expect changes in estrogen and ER-regulated genes or genes thought to play a role in malignant progression/endocrine resistance, but will do this in order to have a consistent assay between PBMC samples and tumor samples as described above. We will describe gene expression over time upon exposure to fulvestrant or the combination of fulvestrant + ganetespib.
- We will describe the frequency of mutations in PIK3CA, ESR1, and other potential genes of interest in archival tumor specimens, cycle 2 Day 9 biopsy specimens, and at the time of progression (when available)
- We will explore the relationship between the presence of a PIK3CA and ESR1 mutations in archival tissue and PFS, in each arm separately
- We will describe mutations in PIK3CA, ESR1, and other potential genes of interest in circulating free DNA (cfDNA) at baseline and time of progression.
- We will explore the relationship between baseline mutations in PIK3CA and ESR1 in circulating cfDNA and PFS, in each arm separately.
- We will tabulate the PIK3CA and ESR1 mutations detected in cfDNA and tumor tissue in order to explore the level of agreement between these two methods
- We will bank any extra materials for future study. We anticipate that this annotated repository will be valuable for future research into the mechanisms of resistance to fulvestrant and to ganetespib.

CONFIDENTIAL

This document is confidential. Do not disclose or use except as authorized.

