We will collect cycle 2 day 9 biopsies (required in patients with biopsy-accessible disease, see Section 3.1.14 and Section 8.1) to assess the effect of fulvestrant alone versus fulvestrant plus ganetespib within tumor specimens. This time point for the research biopsy was chosen to allow adequate time for fulvestrant to reach steady-state levels and to permit HSP90 client proteins modulating growth and survival to be destabilized by ganetespib, thereby inducing downstream transcriptional changes.

We assume that 20% of patients entered on study will have biopsy-inaccessible disease and that biopsies will not be done on these patients. We assume that 60% of patients who undergo biopsies will have informative tissue for analysis. Therefore, we assume that 48% (0.80×0.60) of patients accrued to the trial will have tissue available for this analysis.

We will compare the expression of ER, PR, AR, EGFR, HSF1, and HER2 by immunohistochemistry (IHC) and amplification of EGFR and HER2 using fluorescence in situ hybridization (FISH) to assess the effect of fulvestrant alone versus fulvestrant plus ganetespib within tumor specimens.

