For this analysis, each of the markers will be described as “positive” or “negative”. For ER, PR, AR, and EGFR, “positive” will be defined as $\geq 1\%$ nuclear staining (which includes low positive and well as high positive) and “negative” will be defined as $< 1\%$ nuclear staining. For HSF1, “positive” will be defined as either 2+ staining or 1+ staining, and “negative” as no staining or rare cells positive (Santagata et al, manuscript in preparation). For HER2, we will use the standard 0-3+ scale, where categories 0, 1+, or 2+ count as negative and category 3+ counts as positive. For EGFR and HER2 amplification, FISH ratio ≥ 2.0 will be considered positive and FISH ratio < 2.0 will be considered negative. For each of these eight biologic markers, among patients who have usable tissue from the cycle 2 biopsy, we will test whether the fulvestrant arm or the fulvestrant plus ganetespib arm has a larger percent of patients with the positive category of the marker. This will be done with a two-sided Fisher exact test with significance level of 0.05. The minimal acceptable power was assumed to be 80%. Because of the small sample sizes, sometimes a power between 81% and 84% was the smallest attainable power that was 80% or greater. The power calculations assume that overall (both treatment arms combined), between 35% and 65% of patients would be in the positive category.

The power table below shows the types of differences that could be detected between the arms, given the assumptions above. While the tests are two-sided, because there are only half as many patients on the fulvestrant alone arm as are on the fulvestrant plus ganetespib arm, the differences that have power are slightly different depending on which arm is truly associated with a larger percent of patients with positive biomarker result.

CONFIDENTIAL

This document is confidential. Do not disclose or use except as authorized.

**48% of Patients with Usable Metastatic Tissue: True Treatment Difference
in Percent of Patients with Positive Marker Detectable with *Two-Sided* Fisher Exact Test**

			50% Specimens are Positive			35% are Positive		
N	N with Tissue	Arm with More Patients with “Positive” Marker	N with Positive Marker	Detect. Diff.	True % Positive Marker Combo, Single	N with Positive Marker	Detect Diff.	True % Positive Marker Combo, Single
60	28	Combo	14	58%	71%, 13%	10	54%	55%, 1%
60	28	Single	14	59%	29%, 88%	10	58%	15%, 73%

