All of the other categorical correlative objectives based on the cycle 2 biopsy or (e.g., comparing the two arms by assessing a set of genes using a Nanostring custom code set each categorized as increased, decreased, or neutral) will also be compared using a two-sided Fisher exact test, but it isn’t easy to describe the detectable difference for outcomes that have three categories rather than two categories of biomarker results. Fisher exact tests and descriptive statistics will be used to explore the relationship of biomarker results obtained from different types of specimens (cycle 2 biopsy, archival tissue, CTCs, and optional biopsies at the time of progression), both overall and within treatment arm. With only 28 patients treated on the two arms expected to have usable tissue from the cycle 2 biopsy, and with some of these patients expected to not have usable tissue from the other specimens sources, most of these comparisons will have very little power.

Exploring the relationship of PIK3CA mutations and other oncogenes and PFS in each arm separately may involve a few Kaplan-Meier curves and a few log rank tests, but with only 43 patients treated on both arms combined with a PFS event at the time of analysis, and with some of these patients not having usable biopsy tissue, this exploration may be based mostly on tables of estimated medians of time to PFS event.

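### The gene-expression comparison between arms tests categories of abundance against reference genes, not expression itself, so genes far from the 4-fold cutoffs have essentially no power and others lose power

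*Combined protocol and SAP*

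**What the plan says.** Section 1.4.2 of the protocol uses the cycle 2 biopsies to compare the effect of fulvestrant alone with that of fulvestrant plus ganetespib on a Nanostring gene set. For each gene, "We will use a cutoff of 4-fold increase or decrease relative to standard reference genes" gives the class, and the classes are "upregulated, downregulated, or neutral) for comparison between groups".

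Section 14.5.2 confirms the analysis. It lists comparison of the arms on the "Nanostring custom code set each categorized as increased, decreased, or neutral" among the outcomes to be tested by a two-sided Fisher exact test. For the binary markers in the same section, "This will be done with a two-sided Fisher exact test with significance level of 0.05".

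That section gives detectable differences for binary markers only. For three-category outcomes it says that a detectable difference is not easy to describe. Its remark about very little power refers to comparisons between specimen types.

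No pre-treatment or control-arm value is named as the comparator for the 4-fold rule, and the baseline research biopsy is optional (Sections 5.1.1 and 9.5.2). Section 1.4.2 labels the objective exploratory, and Section 14.5 makes no multiplicity adjustment.

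**The concern.** A 4-fold departure from reference genes within one specimen describes abundance. Section 1.4.2 applies the same classes to archival specimens, which predate study treatment, so the fold cannot be a change from a pre-treatment value. A scarce gene is then classed as downregulated in nearly every patient on both arms, and an abundant gene as upregulated in nearly every patient. The class edges bear no relation to the size of a treatment effect, and the quantitative counts are reduced to three bins.

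At stake is what the cycle 2 biopsy can show about ganetespib's effect in tumour. The biopsy is required in patients with accessible disease, and few usable specimens are expected. A null result for an HSF1 target could mean only that its usual level lies away from the cutoffs, and a useful lead could be dropped.

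**Working it through.** **Inputs from the documents**
- Cutoffs: 4-fold either way, that is ±2 on log2 (Section 1.4.2).
- Test: two-sided Fisher exact test (Section 14.5.2). The 0.05 level is the one stated there for the binary markers.
- Specimens: "With only 28 patients treated on the two arms expected to have usable tissue from the cycle 2 biopsy".

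**Inputs assumed.** The documents give no SD, gene level or expected fold change. I take log2 expression as normal with the same SD in both arms. The SD is 1, with 0.7 and 1.5 as a range. True increases are 2-fold (1 log2), 2.4-fold (1.25 log2) and 4-fold (2 log2). Decreases mirror these results.

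**Step 1: the plan's own figures.** Yield is 0.80 × 0.60 = 0.48, and 0.48 × 60 = 28.8, stated as 28. The table's counts of positives imply 18 combination and 10 single-agent specimens: 18 × 0.71 + 10 × 0.13 = 14.1 and 18 × 0.55 + 10 × 0.01 = 10.0, against 14 and 10 stated. At 18 v 10, exact Fisher power for the four tabled pairs is 0.83, 0.85, 0.84 and 0.79 with the one-sided p-value doubled. It is 0.86, 0.88, 0.93 and 0.86 with the ordinary two-sided version. The doubled version agrees with the stated 80-84% to within about a point. There is no figure to reproduce for the three-category outcome.

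**Step 2: class probabilities.** With mean m, P(down) = Φ((−2 − m)/SD), P(up) = 1 − Φ((2 − m)/SD), and the rest are neutral. Take SD 1 and a true 4-fold increase:
- Arm A mean +4: P(up) is Φ(2) = 0.977 on Arm A and Φ(4) > 0.999 on Arm B. The arms look the same.
- Arm A mean +1: P(up) is Φ(−1) = 0.159 on Arm A and Φ(1) = 0.841 on Arm B. The arms look very different.

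The treatment effect is identical in the two cases.

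**Step 3: power.** The planned test is the exact 2×3 (Freeman-Halton) test, with all tables enumerated. The t-test uses noncentrality (shift/SD)/√(1/18 + 1/10) on 26 degrees of freedom. For a shift of 1 and SD 1 this is 1/0.394 = 2.54. Results at 18 v 10, SD 1, by Arm A mean on log2 relative to the reference genes:

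| True difference | −5 | −4 | −3 | −2 | −1 | 0 | +1 | +2 | +3 | +4 | t-test, any level |
|---|---|---|---|---|---|---|---|---|---|---|---|
| 2-fold | 0.00 | 0.01 | 0.40 | 0.40 | 0.15 | 0.02 | 0.40 | 0.40 | 0.15 | 0.00 | 0.685 |
| 2.4-fold | 0.00 | 0.07 | 0.60 | 0.56 | 0.17 | 0.10 | 0.60 | 0.56 | 0.17 | 0.00 | 0.862 |
| 4-fold | 0.02 | 0.81 | 0.96 | 0.87 | 0.28 | 0.82 | 0.96 | 0.88 | 0.20 | 0.00 | 0.998 |

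At a 19 v 9 split the highest planned-test values are 0.38, 0.58 and 0.95, against 0.66, 0.85 and above 0.99 for the t-test. Between whole log2 levels, the best-placed gene at 18 v 10 reaches 0.46 (2-fold), 0.65 (2.4-fold) and 0.96 (4-fold).

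**Step 4: other SDs (18 v 10, whole log2 levels)**
- SD 0.7: 2-fold, 0 to 0.66 v 0.94; 4-fold, 0 to 1.00 v above 0.99.
- SD 1.5: 2-fold, 0 to 0.21 v 0.37; 4-fold, 0 to 0.69 v 0.90.

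**Step 5: the best case for categories.** The 58-point difference in the plan's binary table, for a gene placed symmetrically across one cutoff, needs a shift of 2 × Φ⁻¹(0.79) = 1.61 SD. The t-test reaches 80% power at 1.15 SD.

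**The case against.** Four points deserve weight.

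- **An arm comparison is planned.** A reader might infer that the plan never compares expression between arms. That goes too far: the classes are compared by Fisher's test. What is missing is a comparison on the expression scale.
- **Large effects are often detected.** With a true 4-fold difference and SD 1, the planned test has 0.81 to 0.96 power at six of the ten levels shown. With SD 0.7, a well-placed gene loses nothing measurable. Section 8 calls HSP72 highly inducible, so large effects are not excluded. This stands, but power is still 0.28 or less at −1 and +3, and near zero at −5 and +4.
- **The t-test is not a cure.** It has only 0.685 power for a 2-fold difference at SD 1. Its constant power across levels rests on a common SD and ignores any detection floor for low counts. It also needs no multiplicity correction only because the plan makes none. At 0.05 per gene, about 5 of every 100 null genes would be flagged, and the platform can carry up to 800 transcripts. The planned Fisher tests are unadjusted too, so multiplicity does not favour them.
- **The objective is exploratory.** Section 8 expects promising findings to be validated later. This limits the consequence, but it does not justify a test that cannot see some genes.

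**Conclusion.** The point holds. The planned test has essentially no power for genes whose usual abundance is far from the cutoffs. For the rest, power is usually lower than that of a direct comparison, and in the scenarios run it was never materially higher. The ranges at SD 1 are 0 to 0.40 v 0.66 to 0.69 (2-fold), 0 to 0.60 v 0.85 to 0.86 (2.4-fold) and 0 to 0.96 v above 0.99 (4-fold), at whole log2 levels with 18-19 v 9-10 specimens. They rest on the assumed SD, effect sizes and normality.

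A reader might infer that most genes are left with little or no power. The documents cannot support that, because they give no gene list, abundance, SD or expected effect. When gene means were assumed normal around 0 or −3 log2 with a spread of 2 to 3, and the SD was 0.7 to 1.5, the share of genes with power below 0.20 was 52-83% for a 2-fold difference but 6-47% for 4-fold. The answer turns on the assumption.

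The primary endpoint, the clinical secondary endpoints and the primary correlative objective are untouched.

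**What to change.** In Sections 1.4.2 and 14.5.2, make the analysis for this objective a between-arm comparison of log2 reference-normalised expression for each gene, by t-test or Wilcoxon test. Report the fold difference between arms with its confidence interval. The Wilcoxon test is the safer choice for low-count genes. Keep the 4-fold classes as descriptive tabulation only.

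A false-discovery rate across the gene set could be reported alongside. This is optional, since the plan's own per-gene tests are also unadjusted.

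The cost is a change of analysis wording. Specimens, assay and data collection stay the same.
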